### **Specific Aims:**

1. Qualitative Approaches across 5-10 groups (n=50-100 total participants), we will:

- a. Deliver an educational intervention on harmful chemical exposures, such as phthalates, found in hair care products, developed by the research team using empirical evidence with key informant feedback.

b. Through focus groups gather participant feedback on content and questions pertaining to intervention and attributes women of color consider when deciding on Hair Care Product use, using a semi-structured guide.

2. Quantitative Approaches using repeat measures, we will:

- a. Using repeated questionnaires to assess PAPM stages, we will assess self-reported behavioral changes in the use of phthalate-free hair care products comparing stage at enrollment to
  - Stage after the intervention (post-test1),
  - Stage at 1- month post-intervention (post-test2), and
  - Stage at 1-month postpartum (post-test3).
- b. Examine the correlation between self-reported behavioral change assessed by the PAPM questionnaire and
  - Change in self-reported Hair Care Product exposure measured via questionnaire (n=50),
  - Change in internal dose of urinary phthalate metabolites (targeted gas chromatography/high resolution mass spectrometry (known as GC/HRMS) Orbitrap; n=25 with 3-repeat samples),
  - (Exploratory) change in internal dose of all-other detectable urinary metabolites (untargeted GC/HRMS-Orbitrap; n=25 with 3-repeat samples).

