## **Specific Aims:**

1. Qualitative Approaches across 5 groups (n=50-100 total participants), we will:

- a. Deliver an educational intervention on harmful chemical exposures, such as phthalates, found in hair care products, developed by the research team using empirical evidence with key informant feedback.
- b. Through focus groups gather participant feedback on content and questions pertaining to intervention and attributes women of color consider when deciding on hair care product use, using a semi-structured guide.

2. Quantitative Approaches using repeat measures, we will:

- a. Using repeated questionnaires to assess PAPM stages, we will assess self-reported behavioral changes in the use of phthalate-free hair care products comparing stage at enrollment to:
  - Stage after the intervention (post-test1),
  - Stage at 1-month post-intervention (post-test2), and
  - Stage at 1-month postpartum (post-test3).
- b. Examine the correlation between self-reported behavioral change assessed by the PAPM questionnaire and
  - Change in self-reported HCP exposure measured via questionnaire (n=50),
  - Change in internal dose of urinary phthalate metabolites (targeted gas chromatography/high resolution mass spectrometry (GC/HRMS) Orbitrap; n=25 with 3-repeat samples),

- (Exploratory) change in internal dose of all-other detectable urinary metabolites (untargeted GC/HRMS-Orbitrap; n=25 with 3-repeat samples).

Questionnaire Constructs : All who wish to enroll and who enroll in the study will be asked to complete the following questionnaires which will be administered preferably via Qualtrix but in paper format if requested.

Eligibility Questionnaire: Confirm that potential participants meet the eligibility requirements (Black or Hispanic women, residing in Northern Manhattan and in the 3rd trimester of pregnancy).

Sociodemographic Questionnaire: Information that includes maternal age, gestational age, race/ethnicity, occupation and educational attainment, and reproductive characteristics and pregnancy details.

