Hair Care Product Questionnaire: Asking participants to take stock of current / recent and past hair care product use. This questionnaire was developed by our colleagues at the Rutgers Center for Environmental Exposures and Disease based on / modified from the Women's Circle of Health Study questionnaire that captured a detailed list (including brand name and product) of each hair product each participant used in the last 24-48 hours. This questionnaire is best completed in the space where the woman conducts her everyday hair care routine as she will need to recall product type and name. Therefore, we are sending the questionnaire to be completed at home prior to the educational intervention.

Precaution Adoption Process Model Questionnaire: A 7-stage theoretical model for health behavior change that attempts to explain how an individual comes to decisions to act and how the individual then translates that decision into action. The 'change in PAPM variable' (PAPM) will illustrate how the intervention moves people across staging. Given movement can be fluid, (Rouillon et al. Int J Environ Res Public Health. 2018;15(10), participants will be categorized as progresses (i.e. advancing stage(s) from last reported stage), regresses (i.e. regressing stage(s) from last reported stage), or stagnant (i.e. not moving from last reported step), comparing: pre-test to post-test1, post-test1 to post-test2, and post-test2 to post-test3, and post-test1 to post-test3. Those who progress to Stage 4 will be labeled as negative progresses. We will provide descriptive statistics by pre-test, post-tests, and by the PAPM variable at each time point (when relevant). Using spearman correlations, we will examine independent correlations between PAPM stage at pre-test with each post-test (post-tests1-3). While PAPM staging is not a continuous parameter but ordinal, (Glanz et al. Health Behavior and Health Education: Theory, Research and Practice 4th Edition; 2008) correlations will inform how the intervention moves people across staging.

The PAPM stages for this study are described as follows:

Stage 1: Never heard of endocrine disrupting chemicals (EDCs), nor EDCs in hair care products (HCPs)

Stage 2: Never thought about using phthalate-free HCPs

Stage 3: Undecided about phthalate-free HCPs

Stage 4: Decided not to use phthalate-free HCPs

Stage 5: Decided to use phthalate-free HCPs

Stage 6: Procured and has used (at least once) phthalate-free HCPs

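### The PAPM change variable omits two of Aim 2a's three comparisons with enrollment, and the Spearman correlation left to cover them does not show direction or amount of movement

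*Combined protocol and SAP*

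**What the plan says.** Aim 2a appears under Specific Aims, both in Study Design and in Procedures. Its wording is "we will assess self-reported behavioral changes in the use of phthalate-free hair care products comparing stage at enrollment to" the stage after the intervention (post-test1), at 1 month post-intervention (post-test2) and at 1 month postpartum (post-test3). Enrollment is the reference for all three.

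The analysis is in the Precaution Adoption Process Model Questionnaire paragraph of Procedures. It has three parts.

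- A change variable, which "will illustrate how the intervention moves people across staging". Women are labelled progresses, regresses or stagnant, "comparing: pre-test to post-test1, post-test1 to post-test2, and post-test2 to post-test3, and post-test1 to post-test3". Progress is defined as "advancing stage(s) from last reported stage". A further rule reads "Those who progress to Stage 4 will be labeled as negative progresses".
- Descriptive statistics by pre-test, by post-test and by the change variable, where relevant.
- Spearman correlations of pre-test stage with the stage at each post-test. The paragraph accepts that stage is ordinal but says these "correlations will inform how the intervention moves people across staging".

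The Statistical Procedures section has an analysis for Aim 1 and one for Aim 2b. It has none for Aim 2a.

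**The concern.** The aim and the change variable do not match. Pre-test to post-test2 and pre-test to post-test3 are two of Aim 2a's three comparisons, and neither is among the four listed intervals. Descriptive statistics by visit would show the group's net shift, and post-test1 to post-test3 would show whether gains at the session last. Neither says how many women have moved from where they stood at enrollment. The descriptive statistics might include a cross-tabulation, but none is clearly promised. That leaves the Spearman correlation as the paired statistic, and the plan's own sentence invites a report of rho as movement.

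The same two intervals matter for Aim 2b, which correlates PAPM change with change in product use and in urinary metabolites. Product use and urine are collected before the session (Phases III and IV) and at two follow-ups (Phase V). Only the PAPM questionnaire is named at the end of the session (The Educational Intervention). If the follow-ups are taken as post-test2 and post-test3, post-test2 to post-test3 is the only listed PAPM interval with product and urine measures at both ends. The plan does not say which PAPM interval Aim 2b uses.

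**Working it through.** The documents give no effect size, power or sample-size calculation for Aim 2a, so there is no figure to reproduce. They also give no expected stage distribution. All stage counts below are assumptions, with n=50 taken from the lower end of the planned 50 to 100.

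**1. Aim against analysis**

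| Aim 2a contrast | In the change variable? | Paired statistic clearly planned |
|---|---|---|
| Pre-test to post-test1 | Yes | Change label, Spearman |
| Pre-test to post-test2 | No | Spearman only |
| Pre-test to post-test3 | No | Spearman only |

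The list does not look like a misprint. The Metabolomics paragraph uses post-test1 to post-test3 again, to prioritise women for the urine subset.

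**2. What rho shows**

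Rho is the Pearson correlation of the midranks, so any shift that keeps the women's order and ties leaves it unchanged.

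*Example A.* Assume 15, 20 and 15 women at Stages 2, 3 and 6, and move only the Stage 3 women.

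| Stage 3 women | rho | Number at Stage 5 or above |
|---|---|---|
| Stay at 3 | 1.00 | 15 |
| All to 4 (decided not to use) | 1.00 | 15 |
| All to 5 (decided to use) | 1.00 | 35 |

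*Example B.* Assume 15, 15 and 20 women at Stages 1, 2 and 3. All Stage 1 women move to Stage 2, since nobody should remain unaware after the session. The Stage 3 women stay at 3, go to 4 or go to 5.

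- Pre-test midranks are 8, 23 and 40.5. Deviations from the mean rank of 25.5 are −17.5, −2.5 and 15.
- Post-test midranks are 15.5 (30 women) and 40.5 (20 women). Deviations are −10 and 15.
- Sum of products: 15(175) + 15(25) + 20(225) = 7,500.
- Sums of squares: pre-test 15(306.25) + 15(6.25) + 20(225) = 9,187.5; post-test 30(100) + 20(225) = 7,500.
- rho = 7,500 / √(9,187.5 × 7,500) = 0.90 in all three cases. The number at Stage 5 or above is 0, 0 and 20.

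*Example C.* This one lets women at the same stage behave differently. Assume baseline Stages 1 to 7 at 30/25/20/3/10/7/5%. Each woman at Stages 1 to 3 moves to the target stage with the stated probability, unmoved Stage 1 women go to Stage 2, and the rest stay. There were 4,000 simulated samples of 50 per scenario.

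| Scenario | Mean rho | Expected change at Stage 5 or above |
|---|---|---|
| No other movement | 0.93 | 0 |
| Half of Stages 1–3 to Stage 4 | 0.65 | 0 |
| Half of Stages 1–3 to Stage 5 | 0.53 | 0.5 × 75 = 37.5 points |

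The sampling SD of rho in the last two rows is 0.11 to 0.12, about the size of the gap between them (0.65 − 0.53 = 0.12). One observed rho would not reliably tell movement to rejection from movement to adoption. The lowest mean rho also belongs to the most favourable outcome.

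**3. Whether the listed labels recover the missing contrasts**

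Four visits and seven stages give 7⁴ = 2,401 paths. Require every post-test to be at Stage 2 or above and no rise into Stage 6 or 7 by post-test1. Then 42 − 11 = 31 pre-test/post-test1 pairs remain, and 31 × 6 × 6 = 1,116 paths. Group these by their labels over the four listed intervals.

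| Labels | Patterns | Direction from pre-test to post-test2 undetermined | Direction from pre-test to post-test3 undetermined |
|---|---|---|---|
| Three | 39 | 10 | 10 |
| With *negative progresses* as a fourth | 84 | 24 | 24 |

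For example, paths 2-5-3-3 and 3-5-3-3 both read progresses, regresses, stagnant, regresses. From enrollment to either later post-test, the first woman has gained a stage and the second has not moved. These are counts of patterns, not probabilities.

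**The case against.** The best reply is that little is lost. This is an uncontrolled pilot with no stated hypothesis test for Aim 2a, the stages are recorded at every visit, and the planned descriptive statistics will show the stage distribution each time. The stepwise intervals are deliberate, because the plan notes that movement can be fluid. Most label patterns (39 − 10 = 29 of 39) do fix the direction from enrollment, including progress that is then kept or extended, which is the course the plan hopes for. Rho is not blind to movement either: in Example C it falls from 0.93 to 0.65 or 0.53. Examples A and B need every woman at a given stage to move alike. The plan also claims only that correlations inform movement, not that they measure it.

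On Aim 2b, post-test1 follows a session of at most 2.5 hours, so pre-session product use and urine could fairly serve as the starting values for post-test1. The urine-subset rule points to post-test1 to post-test3.

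Much of this stands. The gap is recoverable, the pattern counts do not size it, and rho does respond when women move differently. But rho does not distinguish adoption from rejection, and marginal distributions do not give within-woman change. The ambiguous patterns are those with opposing moves, such as a gain at the session that later fades, and the later contrasts exist to describe that. The urine rule selects women; it does not pair a PAPM interval with an exposure change. If pre-session exposure is to stand in for post-test1, the plan should say so.

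**Conclusion.** The concern holds and should be fixed. One of Aim 2a's three enrollment contrasts is covered by the change variable. The other two are left with a correlation to which the plan gives a meaning it does not have. That conclusion rests on the text and on a property of rank correlation, and not on the assumed stage counts. The counts serve only to show scale: the same rho of 1.00 with 15, 15 or 35 of 50 women at Stage 5 or above.

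The Aim 2b point further assumes that the two follow-ups correspond to post-test2 and post-test3. Because stages are collected at every visit, the fault is in the analysis plan and can be corrected without touching data collection.

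**What to change.** - Add pre-test to post-test2 and pre-test to post-test3 to the change variable. Keep the stepwise intervals and the *negative progresses* label.
- Define each label as change from the earlier to the later visit of the named interval. A definition relative to the last reported stage does not fit an enrollment contrast, nor post-test1 to post-test3.
- For each enrollment contrast, report the number of women with both measurements, the transition table, and the proportions progressing, regressing, stagnant and *negative progresses* with 95% confidence intervals. Also report the paired change in the proportion at Stage 5 or above with its interval. That cut-point is not in the plan and counts a decision to use as well as use, so it supplements the transition table. No added hypothesis tests are needed.
- Delete the sentence saying that the correlations inform movement. Drop the pre/post Spearman or label it as rank stability only.
- Keep Spearman for Aim 2b, and state which PAPM interval is paired with each change in product use and urine.

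The cost is a few lines of text and slightly more descriptive analysis, with no new data, visits or participants. The summaries are workable at n=50. With assumed counts, 25 of 50 progressing is 50% (exact 95% CI 36 to 64). If 15 women move to Stage 5 or above and 3 move out, the change is (15 − 3)/50 = +24 points. The standard error is √(18 − 12²/50)/50 = 0.078, giving a Wald 95% CI of 9 to 39 points.

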## **Statistical Procedures**

For the Pilot Intervention:

Aim 1 Analysis. All sessions (whether conducted in person or remote via Zoom) will be recorded and transcribed verbatim by a professional transcription service. We will use Dedoose to code using grounded theory and qualitative content analysis focusing on the questions and content feedback of the educational intervention and attributes pertaining to PCP use. [name] will oversee the creation of the codebook and train the research staff involved in coding transcripts. We believe with n=50-100, we will meet our goal of saturation and finalized thematic codes will aid in improving the educational intervention and provide an exhaustive categorization of attributes WOC consider for HCP product selection.

**Aim 2b Analysis:** Please see Study Procedures section (under ‘Metabolomics’ heading) for an explanation of [name] and his team at Brown University’s involvement in the analysis portion of this study. In brief, this exploratory analysis, performed by our partner collaborators at Brown University, will conduct Hair Care Product descriptive analyses, including the frequency of phthalate-containing products, by category and overall. They will conduct urinary phthalate descriptive analyses (log transformed concentrations) comparing detectable ranges for each of the urinary phthalate exposure constructs and comparing with national levels from biomonitoring reports. They will also conduct untargeted descriptive analyses by characterizing the patterns in chemical exposures over time through principle component analyses (PCA) (Gibson et al. Current environ health reports. 2019;6(2):53-61). Using spearman correlations, they will independently examine the correlation between PAPM and a) change in phthalate containing PCPs, and b) change in PCA patterns. **Results:** We expect the intervention will result in an association between PAPM progresses and a decreased use of phthalate-containing HCPs and lower concentration levels of MEP (and LMW metabolites).

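### The Stage 4 rule covers only moves up into refusal, leaves the Aim 2b Spearman order undefined, and is paired with a pre/post stage correlation that cannot show movement

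*Combined protocol and SAP*

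**What the plan says.** The rules are in the Procedures section, under Specific Aims, in the paragraph on the Precaution Adoption Process Model Questionnaire and the stage list after it.

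- Scale. Three neighbouring stages read "Stage 3: Undecided about phthalate-free HCPs", "Stage 4: Decided not to use phthalate-free HCPs" and "Stage 5: Decided to use phthalate-free HCPs". The staging is described as ordinal: "While PAPM staging is not a continuous parameter but ordinal".
- Change variable. Women are classed by the direction of the stage number, for example "progresses (i.e. advancing stage(s) from last reported stage". A fall is regress and no move is stagnant. The single exception is "Those who progress to Stage 4 will be labeled as negative progresses".
- Stage correlations. "Using spearman correlations, we will examine independent correlations between PAPM stage at pre-test with each post-test (post-tests1-3"). The same paragraph says that these correlations will show how the intervention shifts women between stages. It states no recoding of Stage 4.
- Aim 2b. Under Statistical Procedures, the collaborating analysts will use Spearman correlations: "they will independently examine the correlation between PAPM and a) change in phthalate containing PCPs, and b) change in PCA patterns". PAPM is the name that the Procedures section gives to the change variable. Neither section gives a numeric order for its four labels.

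**The concern.** The PAPM numbering is not monotone in adoption at Stage 4. A woman who has decided against the products carries a higher number than one who is still undecided. The authors saw this and gave upward moves into Stage 4 their own label, but the correction stops there. Three things remain open:

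1. Leaving refusal for indecision is recorded as a step back.
2. A rank correlation is planned on a variable with four labels and no stated order.
3. The stage-by-stage correlation is offered as evidence of movement, which it does not measure.

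Stage movement is the Aim 2a outcome and one side of every Aim 2b correlation. At stake are whether the pilot's main behavioural result can be read at all, and whether its Aim 2b coefficient is fixed before the data are seen.

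**Working it through.** The plan states no figure on this point, so there is none to reproduce.

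**Step 1: labels.** Applying the rules literally to all 7 × 7 = 49 stage pairs gives 18 progress, 3 negative progress, 7 stagnant and 21 regress (18 + 3 + 7 + 21 = 49). The three negative-progress pairs are 1, 2 and 3 to 4. The other three routes into Stage 4 (from 5, 6 or 7) are plain regress. A 4-to-3 move is regress, 4-to-5 is progress, and 4-to-4 is stagnant.

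**Step 2: pre/post stage correlation.** Spearman's rho is the Pearson correlation of the two sets of ranks, with mid-ranks for ties. Any strictly increasing change applied to everyone leaves the ranks, and so rho, unchanged. For illustration, assume 50 women with pre-test counts of 15, 15, 12, 3, 3, 2 and 0 in Stages 1 to 7. The documents give no distribution.

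| Scenario | rho, stages as numbered | rho, Stage 4 placed just below 3 | Mean stage change | Share at Stage 5 or above, pre to post |
|---|---|---|---|---|
| Nobody moves | 1.000 | 1.000 | 0 | 5/50 = 10% to 10% |
| All 12 undecided reject (3 to 4) | 0.993 | 0.993 | 12 × 1/50 = +0.24 | 10% to 10% |
| All 12 undecided accept (3 to 5) | 0.959 | 0.993 | 12 × 2/50 = +0.48 | 10% to 17/50 = 34% |
| Everyone moves up one stage | 1.000 | not needed | +1.00 | 10% to 8/50 = 16% |

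As numbered, mass rejection gives a slightly higher rho than mass acceptance, and no movement cannot be told from universal movement. Placing Stage 4 just below Stage 3 gives rejection and acceptance the same value. Placing it lowest of all does separate them (0.153 against 0.993), but acceptance at 0.993 is still next to the 1.000 for no movement. The share at Stage 5 or above tells acceptance (34%) from rejection (10%) directly.

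**Step 3: Aim 2b correlation.** The plan gives n=50 for the questionnaire correlation. All other inputs are assumptions: 40% progress with a 1 SD fall in use, 20% negative progress with no change, 30% stagnant with no change, and 10% regress. Regressers' use is either unchanged or 0.5 SD higher. Mean simulated rho:

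| Negative progress ranked | Regressers unchanged | Regressers +0.5 SD |
|---|---|---|
| With progress | about -0.29 | about -0.35 |
| Below regress | about -0.39 | about -0.42 |
| With stagnant | about -0.41 | about -0.48 |

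Placement alone accounts for 0.41 - 0.29 = 0.12 in the first column and 0.48 - 0.35 = 0.13 in the second. The rest of the range from -0.29 to -0.48 comes from the assumption about regressers. At 5% rejection the spread from placement is about 0.03 to 0.04, depending on how the freed share is reallocated. The sampling SD of rho at n=50 is about 0.11. The with-stagnant placement gives the strongest coefficient partly by construction, because rejecters were assigned no change in use.

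**Step 4: knock-on.** The Metabolomics paragraph gives urine-assay priority to women classed as progress or stagnant between post-test 1 and post-test 3. It does not say whether negative progress qualifies, and under the present rule a 4-to-3 mover falls outside the priority group.

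**The case against.** A reader might infer that women who reject the products count as moving toward adoption in the Spearman analyses. The documents do not support this, for three reasons. The change variable separates upward moves into Stage 4 from ordinary progress. No text scores those women as progress in Aim 2b; their position is simply unstated. And a correlation of pre-test with post-test stage has no direction, so a rejecter gets a higher rank than an undecided woman but is not credited with movement.

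The other side has further points. Descriptive statistics by time point and by the change variable are planned, so the frequency of negative progress should be visible. The Aim 2b work is described as exploratory, in a pilot. The rejection rate is unknown; if it is near 5%, the coding effect is small against sampling error, and all the simulated means stay negative. The 4-to-3 rule affects only women already in Stage 4, and their number is not known either.

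These points limit the size of the Aim 2b problem. They do not supply the missing order or change the label on a 4-to-3 move. Nor do they make the pre/post correlation a measure of movement, and that last fault does not depend on how many women reach Stage 4.

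**Conclusion.** The point holds in three parts.

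- The Stage 4 exception is one-sided: it covers three of the six routes into Stage 4, and a 4-to-3 move is recorded as regress. This follows from the text with no assumption.
- The Aim 2b Spearman has no defined order for negative progress. That gap is also a matter of text. Its size is illustrative: placement shifts mean rho by about 0.12 to 0.13 at 20% rejection and about 0.03 at 5%, under assumed shares and effects.
- The pre-test/post-test stage Spearman measures preservation of rank order and cannot do what the plan says it will, however Stage 4 is coded. The invariance is a property of the statistic; only the values 0.993 and 0.959 depend on the assumed distribution.

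The third part matters most, because following the plan as written would give a misleading reading of Aim 2a. The change should be made before the stage data are analysed.

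**What to change.** Revise the analysis text as follows. No new data are needed.

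1. **Aim 2a.** Summarise movement by the paired change from enrollment to each post-test in the share at Stage 5 or above, with a confidence interval and a stage-transition table. Do not read the pre/post Spearman as movement.
2. **Stage 4 as a side branch.** Do not label 4-to-3 as regress; group it with stagnant. Keep 5, 6 or 7 to 4 as regress, so that abandoning a decision to use is not softened. Report entry to and exit from Stage 4 separately.
3. **Aim 2b.** Fix the order in advance as regress, then stagnant and negative progress tied, then progress. Add a sensitivity analysis with negative progress placed lowest.

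Because item 2 changes who is classed as stagnant, the Metabolomics paragraph should also say whether negative progress and 4-to-3 movers fall in the urine-assay priority group.

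The cost is a slightly longer analysis and one added summary measure, which goes beyond a pure recoding rule and should be declared as an addition.
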